3.2. Study Endpoints

3.2.1. Primary Endpoints

3.2.1.1. Pharmacokinetic Endpoints

Pharmacokinetic endpoints for the study are:

- Area under the plasma concentration versus time curve (AUC) from time 0 to 48hours after dosing (AUC_{0-48})
- AUC from time 0 to the last quantifiable concentration (AUC_{last})

- AUC from time 0 extrapolated to infinity (AUC_{0-inf})
- Maximum observed plasma concentration (C_{max})
- Time to reach maximum observed plasma concentration (T_{max})
- Elimination half-life associated with the terminal slope of the semilogarithmic concentration-time curve ($T_{1/2}$)
- Apparent volume of distribution (V_d) after iv administration only
- Systemic clearance (CL) after iv administration only

3.2.2. Secondary Endpoints

3.2.2.1. Safety Endpoints

The safety endpoints of this study will be assessed through:

- The incidence of treatment-emergent adverse events (TEAEs), relationship to the study drug, and severity
- Serious adverse events (SAE) and adverse events (AE) leading to discontinuation of study drug
- Clinical laboratory test results (hematology and serum chemistry)
- Vital sign measurements (systolic blood pressure, diastolic blood pressure, heart rate [HR], and oral body temperature)
- Physical examination findings

4. General Statistical Considerations

All statistical analyses will be conducted using statistical analysis system SAS® Version 9.4 or higher (SAS Institute, Cary, NC).

Descriptive statistics for continuous variables will be summarized using descriptive statistics (number of subjects (n), mean, median, standard deviation (SD), minimum, and maximum). For categorical variables, frequencies and percentages will be presented.

During the analysis and reporting process, any deviations from the statistical analysis plan designed for this protocol will be described and justified in the final clinical study report (CSR).

Unless specified otherwise, baseline will be defined as the last non-missing assessment (including repeated and unscheduled assessments) prior to the study drug administration for each treatment period.

For summary of safety assessments, if there are repeated measurements at a time point, the first non-missing assessment at that time point will be used in the summary tables.

Unscheduled results will not be included in the summary tables, except for determining Baseline, but will be presented in data listings.

The methodology and data handling specifications for PK data are detailed in Section 8.

4.1 Sample Size

The sample size selected is based on an estimation approach rather than a formal hypothesis testing approach. An estimation approach with 20 subjects in each age cohort (10 subjects per treatment, per age cohort) will be enrolled. A total of 40 subjects will be enrolled so that at least 24 subjects are evaluable for PK parameter estimation (with a minimum of 6 subjects per treatment, per age cohort).

4.2 Analysis Populations

Pharmacokinetic (PK) Evaluable Population: The PK evaluable population (PK population) will include subjects who received study drug and have at least 1 evaluable PK parameter. Where subjects experience issues which may affect exposure to study drug (eg, emesis, dosing errors, etc), data will be reviewed by the study pharmacokineticist and evaluated for exclusion from the PK population on a case-by-case basis.

All subjects excluded from the PK population will be documented in the data listings.

The safety population will consist of all assigned subjects who received study drug.

5. Subject Disposition

5.1 Disposition

The following will be summarized for the enrolled population by treatment and total within each cohort, for all the enrolled subjects:

The number of subjects who completed the study

- The number of subjects who did not complete the study (both overall and according to reasons for discontinuation from the study)
- The number of subjects in each analysis population
- Reason for discontinuation

Subject disposition data will be summarized in a table and presented in a data listing.

5.2 Protocol Deviations

Investigators will agree to apply due diligence to avoid protocol deviations. All significant protocol deviations will be recorded and reported in the CSR.

Significant protocol deviation will be defined as a subset of protocol deviations that will lead to a subject being discontinued from the study, or significantly will affect the subject's rights, safety, or well-being and/or the completeness, accuracy, and reliability of the study data.

Significant protocol deviations will be summarized by treatment and total within each cohort for the Safety population. All protocol deviations will be presented in a data listing.

5.3 Inclusion and Exclusion Criteria

Inclusion and exclusion criteria deviations will be presented in a data listing.

6. Subject Demographics/ Other Baseline Characteristics

6.1 Subject Demographics

Descriptive statistics will be calculated for the following continuous demographic characteristics:

- Age (years)
- Weight (kg)
- Height (cm)
- Body mass index (BMI) (kg/m²)

Frequency counts and percentages will be tabulated for the categorical variables:

- Sex
- Ethnicity
- Race

The summaries will be presented by treatment and total within each cohort for the safety population.

Demographic information collected at screening will be presented in a data listing.

6.2 Medical History

The medical history data will be coded using the Medical Dictionary for Regulatory Activities (MedDRA, version to be delineated in the clinical study report [CSR]) and presented in a data listing.

7. Therapy

7.1 Prior and Concomitant Therapies

Prior and concomitant therapies will be coded using the latest version of the WHO Drug Dictionary. Treatments that have been administered within the 72 hours prior to the date of informed consent and pediatric assent, or during the Screening phase, will be recorded in the eCRF.

Medication Therapy that stop prior to the first dose of study drug will be classified as prior therapy. Therapy that start on or after the first dose of study drug will be classified as concomitant. If a therapy starts before the first dose of study drug and stops on or after the first dose of study drug, then the therapy will be classified as both prior and concomitant.

All prior and concomitant therapy will be summarized by treatment within each cohort and total within each cohort for the safety population and presented in a data listing.

7.2 Medical or Surgical Treatment Procedures

Medical or surgical treatment procedures will be presented in a data listing.

7.3 Study Treatment

The study drug administration data as collected on eCRF will be presented in a data listing.

8. Pharmacokinetic Analysis

All PK listings and individual concentration-time profiles will be presented using the safety population. PK tables and mean figures will be presented using the PK population.

8.1 Data Handling

Data rounding specifications for PK data are documented in the PK TLF shells. For the PK analysis, below the limit of quantification (BLQ) values before the first quantifiable concentration will be treated as zero. Below the limit of quantification values after the first quantifiable concentration will be set as missing. Missing concentrations will be treated as missing. If consecutive BLQ concentrations are followed by quantifiable concentrations in the terminal phase, those concentrations after BLQ concentrations will be treated as missing.

For concentration summary statistics, BLQ values before the first quantifiable concentration will be treated as zero. Below the limit of quantification values after the first quantifiable concentration will be set as missing and excluded from the summary statistics. Mean BLQ concentrations will be presented as BLQ, and the standard deviation (SD) and coefficient of variation (CV) will be reported as not applicable for descriptive statistics, if all individual values are BLQ. Missing concentrations will be treated as missing.

8.2 Plasma Concentrations

Serial blood samples will be collected from all subjects at the following time points for PK assessment of omadacycline:

Oral Treatment

- At least 15 minutes prior to administration of oral omadacycline 300 mg and at 1, 2, 3, 8, 24, and 48 hours after dosing.

Intravenous (IV) Treatment

- At least 15 minutes prior to infusion of IV omadacycline 100 mg, and at 10 minutes, and 0.5, 1, 2, 8, 24, and 48 hours after the end of the IV infusion.

The permitted windows for PK sample collection are as follows:

Pharmacokinetic time points	Window
Pre-dose	at least 15 minutes before study drug administration
10 minutes to 3 hours	± 5 minutes
8 to 48 hours	± 1 hour (60 minutes)

PK collections that have an actual sampling time that deviates from the predefined collection time windows will be flagged in the data listings and excluded from the calculation of concentration summary statistics.

Individual plasma concentrations of omadacycline and time deviation data will be presented in data listings. Plasma concentration data will be summarized by scheduled time point for each treatment and age cohort using descriptive statistics (number of observations (n), arithmetic mean (mean), standard deviation (SD), coefficient of variation (CV), median, minimum, and maximum).

Individual plasma concentrations of omadacycline will be plotted by treatment, age cohort, and actual time (relative to the start of infusion for the IV Treatment) on both linear and semi-logarithmic scales. Mean plasma concentrations will be plotted by nominal time (relative to the start of infusion for the IV Treatment) on both linear and semi-logarithmic scales with both treatments and age cohort overlaid on the same plots.

8.3 Plasma Pharmacokinetic Parameters

Plasma concentration-time data will be analyzed by non-compartmental analysis using Phoenix® WinNonlin® Version 8.3 or higher (Certara USA, Inc., Princeton, NJ). The following PK parameters will be calculated for omadacycline, where data permit:

C_{max}	Maximum observed plasma concentration.
T_{max}	Time to reach maximum observed plasma concentration.
AUC_{0-48}	AUC from time 0 to 48 hours postdose, calculated using the linear trapezoidal rule.
AUC_{last}	AUC from time 0 to the last quantifiable concentration (C_{last}), calculated using the linear trapezoidal rule.
AUC_{0-inf}	AUC from time 0 extrapolated to infinity, calculated as $[AUC_{last} + (C_{last} / \lambda_z)]$.
$T_{1/2}$	Elimination half-life associated with the terminal slope of the semilogarithmic concentration-time curve, calculated as: $\ln(2) / \lambda_z$.
CL	Systemic clearance, calculated as: Dose / AUC_{0-inf} (after iv administration only)

V_z	Apparent volume of distribution during the terminal phase, calculated as: $\text{Dose} / [\lambda_z * \text{AUC}_{0-\text{inf}}]$ (after iv administration only).
-------	---

In addition to the above PK parameters, which will be listed and summarized, the following parameters will also be listed to document the selection of data points used to estimate $t_{1/2}$ using non-compartmental procedures:

λ_z	Apparent terminal elimination rate constant, where λ_z is the magnitude of the slope of the linear regression of the log concentration versus time profile during the terminal phase.
Number of points	Number of data points used to estimate λ_z ; a minimum of 3 data points must be used, and C_{max} must not be included.
λ_z lower	Lower bound used for the estimation of λ_z .
λ_z upper	Upper bound used for the estimation of λ_z .
Rsq	Regression coefficient of determination (goodness of fit statistic); λ_z and all associated parameters will only be reported where $\text{Rsq} \geq 0.80$.
%AUC _{ext}	Percentage of AUC _{0-inf} due to extrapolation. AUC _{0-inf} , CL and V_z values will be flagged and excluded from summary statistics where %AUC _{ext} > 20%.

Actual sampling times (relative to the end of infusion for the IV Treatment) will be used for the estimation of all plasma PK parameters, and all concentrations will be included in the analysis (including concentrations collected outside predefined collection windows).

Plasma PK parameters of omadacycline will be presented in data listings and summarized separately by treatment and age cohort using descriptive statistics (number of observations (n), arithmetic mean, SD, CV, geometric mean, geometric CV, median, minimum, and maximum). T_{max} will be summarized using number of observations, median, minimum, and maximum only.

9. Safety Analysis

The purpose of this section is to define the safety parameters for the study. All summaries of safety data will be conducted using the Safety population. Safety assessments will include monitoring of adverse events (AEs), clinical laboratory test results, vital sign measurements, and physical examination findings.

All safety summaries and analyses will be conducted for the Safety Analysis Set. All safety data will be presented in listings.

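### SAP 8.3 uses the linear trapezoidal rule across 16 h and 24 h gaps in the declining phase, which overstates AUC, more so the shorter a subject's half-life

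*SAP*

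**What the plan says.** SAP 8.3 gives AUC0-48 as "AUC from time 0 to 48 hours postdose, calculated using the linear trapezoidal rule". AUClast is likewise "calculated using the linear trapezoidal rule". AUC0-inf adds the extrapolated tail, Clast divided by lambda-z, to AUClast. CL is dose over AUC0-inf, and Vz also divides by AUC0-inf, so all three inherit the rule. Neither document provides a logarithmic rule for falling segments. Protocol 12.7.1 specifies only noncompartmental analysis and the software.

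SAP 8.2 puts the oral samples "at 1, 2, 3, 8, 24, and 48 hours after dosing" and the IV samples "at 10 minutes, and 0.5, 1, 2, 8, 24, and 48 hours after the end of the IV infusion". In both arms the late gaps are 16 h (8 to 24 h) and 24 h (24 to 48 h). The gap before them is 5 h for oral (3 to 8 h) and 6 h for IV (2 to 8 h).

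Two other rules in SAP 8.3 bear on the point. Lambda-z comes from a regression of log concentration on time, for which "a minimum of 3 data points must be used", without Cmax. For the IV arm, "Actual sampling times (relative to the end of infusion for the IV Treatment) will be used for the estimation of all plasma PK parameters".

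**The concern.** If concentrations fall exponentially, the straight line between two samples always lies above the curve. The excess depends on how many half-lives the gap spans, so it is larger in subjects who eliminate faster. It is a systematic error that more subjects will not average away. It also narrows real differences in AUC and CL between subjects.

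AUC is a primary endpoint (SAP 3.2.1). The study is meant to establish paediatric dosing by reference to adults (Protocol 3 and 7.3). Protocol 12.5 has PK compared with the established adult profile during the study, and that review may lead to an amendment. An avoidable bias of several percent in AUC feeds directly into that comparison.

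**Working it through.** **Inputs.** Sampling times and rules are those of SAP 8.2 and 8.3. The documents state no half-life, AUC or bias figure, so there is no plan figure to reproduce. Half-lives of 10 to 24 h are assumed. Curves are noise-free and sampled at nominal times.

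**One gap.** For a mono-exponential decline with rate k = ln 2 / half-life over a gap of length D:

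linear area / true area = (kD/2) / tanh(kD/2)

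At a half-life of 12 h, k = 0.0578 per hour.
- 8 to 24 h: kD/2 = 0.462, tanh = 0.432, ratio 1.070.
- 24 to 48 h: kD/2 = 0.693, tanh = 0.600, ratio 1.155.

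**From gap to AUC0-48 (IV, one phase, 12 h, starting concentration 1).**
- 8 to 24 h: linear 16 × (0.630 + 0.250)/2 = 7.040; true (0.630 - 0.250)/0.0578 = 6.578; excess 0.462.
- 24 to 48 h: linear 24 × (0.250 + 0.0625)/2 = 3.750; true (0.250 - 0.0625)/0.0578 = 3.246; excess 0.504.
- True area from the 10 min sample to 48 h is 16.06, so the two gaps add (0.462 + 0.504)/16.06 = 6.0%. The earlier intervals bring the total to 6.3%.

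**Across half-lives.** Oral curves are one-compartment with absorption half-lives of 0.5 to 1.5 h. IV area here runs from the 10 min sample.

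| Assumed half-life | Ratio 8-24 h | Ratio 24-48 h | AUC0-48 error, IV one-phase, linear | AUC0-48 error, oral, linear | AUC0-48 error, oral, linear-up/log-down |
|---|---|---|---|---|---|
| 10 h | 1.100 | 1.221 | +8.1% | +6.0 to +7.2% | -2.4 to -1.0% |
| 12 h | 1.070 | 1.155 | +6.3% | +4.4 to +5.5% | -2.1 to -0.9% |
| 16 h | 1.040 | 1.089 | +4.1% | +2.4 to +3.4% | -1.8 to -0.7% |
| 20 h | 1.025 | 1.057 | +2.8% | +1.3 to +2.3% | -1.6 to -0.6% |
| 24 h | 1.018 | 1.040 | +2.1% | +0.7 to +1.6% | -1.4 to -0.5% |

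Linear-up/log-down is exact for the one-phase IV curve from the 10 min sample. For oral dosing, missed area around the peak makes it slightly negative and also offsets part of the linear rule's excess.

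**IV with a distribution phase.** The 2 to 8 h gap now contributes too. With up to 25% of AUC in a fast phase (half-life 0.5 to 2 h), the linear rule overstates AUC0-48 by up to 14.5% at 10 h and 12.0% at 16 h. The steepest model tried (fast half-life 2 h, amplitude ratio 4, so 8/(8 + 10) = 44% of AUC in the fast phase at 10 h) gives +16.8%. Linear-up/log-down leaves at most about +6% in the two-phase cases. Measured from the start of infusion, the ranges are about +2 to +13% (linear) and -1 to +3% (linear-up/log-down).

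**Carry-over to CL (IV, one phase).** AUC0-inf is too high by 5.9% at 12 h, 3.6% at 16 h and 2.3% at 20 h. CL is then too low by 1 - 1/1.059 = 5.6%, and likewise 3.4% and 2.2%. AUC0-inf, CL and Vz "will be flagged and excluded from summary statistics where" extrapolation exceeds 20%, which on this schedule happens above a half-life of about 21 h. The summarised values therefore come from the shorter half-lives, where the bias is larger.

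**Time origin.** With IV time counted from the end of infusion and concentration taken as zero there, 1.0-4.6% of the area is left out. Against the true area from the start of infusion, the linear rule's net error is then +0.8 to +5.6% (one phase, or fast half-life 1 h with amplitude ratio 2; 10-24 h). It is -0.3 to -0.8% with a steeper fast phase (0.5 h, ratio 4; 16-20 h). Linear-up/log-down alone, with the origin unchanged, gives -1.1 to -4.2%.

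**The case against.** The linear rule is prespecified and reproducible. The study is descriptive: the sample size rests on estimation (SAP 4.1), no formal comparisons are planned (Protocol 12.10), and a cell may hold as few as 6 evaluable subjects. Individual concentrations are listed, so anyone can recompute AUC by another rule. All of this stands. It limits the consequences but does not remove a predictable bias from the summarised primary endpoint.

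The replacement is not uniformly better. For oral dosing with a 1.5 h absorption half-life, linear-up/log-down gives -1.6% at 20 h and -1.4% at 24 h, against +1.3% and +0.7% for the linear rule. For IV, part of the overstatement is currently masked by the end-of-infusion origin, so changing the rule alone would trade a positive error for a negative one. Both points stand and shape the fix. An offset from a separate defect is not a reason to keep the linear rule.

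Three stronger readings are tempting, and the documents do not support them:
- A reader might infer that children have short half-lives and are therefore the most affected. The only text on age (Protocol 3 and 5.2, SAP 1) says that PK in this class differs little between adults and children.
- A reader might infer that the bias cannot cancel against adult values because adults were sampled more densely. Neither document gives the adult sampling times or AUC rule. If the adult values also used the linear rule, changing it here alone could reduce comparability.
- A reader might see a contradiction between log-linear regression for lambda-z and linear AUC. The two choices sit awkwardly together, but the first does not oblige a log rule for the second.

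**Conclusion.** The concern holds as a systematic, avoidable overstatement of AUC, with CL understated to match. The direction is secure for an exponentially declining phase. The size depends on half-lives that the documents do not give. Over an assumed 24 down to 10 h, AUC0-48 is overstated by about 1-7% for oral dosing, about 2-8% for IV with little distribution phase, and up to about 13-15% for IV with a marked one.

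A single figure such as 10% should be read neither as a ceiling nor as typical. At an assumed 8 h, one-phase IV reaches +10.6%, and the steepest two-phase model exceeds 15%. At 16-20 h, one-phase IV is +2.8 to +4.1%. The effect belongs to any subject with a shorter half-life, not to an age group. This is worth correcting because correction is cheap, but it does not undermine the study.

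**What to change.** In SAP 8.3, replace the linear trapezoidal rule by the linear-up/log-down trapezoidal rule for AUC0-48 and AUClast; AUC0-inf, CL and Vz then follow. In the same revision, measure IV time from the start of infusion, so that the infusion-phase area is included and one error is not exposed by removing the other. State which rule the adult comparison values used and, if it was linear, also report linear-rule AUC alongside.

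The cost is a software setting, revised SAP wording and possibly one extra set of AUC summaries. No new data or blood samples are needed. The price in accuracy is a small negative oral bias (about -2.4 to -0.5% over the assumed range), with no net gain for oral dosing at half-lives of about 20 h or more when absorption is slow.

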7.5 Test Article Administration

7.5.1 Administration of Oral and IV Treatment

Subjects will receive a single dose of either IV or oral test article on Day 1.

Oral Omadacycline

All doses of oral test article should be taken with water.

All oral doses should be taken in a fasted state. Fasting is defined as no food, antacids, or multivitamins containing multivalent cations (e.g., aluminum, magnesium, calcium, bismuth, iron, or zinc) or drink except water for at least 6 hours before dosing. After dosing, no food is permitted for 2 hours and no dairy products, antacids, or multivitamins containing multivalent cations (e.g., aluminum, magnesium, calcium, bismuth, iron, or zinc) for 4 hours.

IV Omadacycline

Infusion of IV test article in 100 mL normal saline solution will be administered continuously over approximately 30 minutes. Infusion start and stop times are to be recorded in the source documents and on the eCRF.

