3.1. Overall Study Description

This is a Phase 1, open-label, multi-center study in children and adolescent subjects (males and females, 8 to < 18 years of age) with suspected or confirmed bacterial infections who are receiving concomitant systemic antibacterial therapy.

This study will consist of 2 age cohorts:

- Cohort 1 (adolescents): 12 to < 18 years of age
- Cohort 2 (children): 8 to < 12 years of age

Subjects will undergo screening evaluations to determine eligibility within 48 hours prior to dosing. Approximately 40 subjects (20 per age cohort) will be enrolled.

On Day 1, per Principal Investigator (PI) discretion, subjects will receive a single dose of either intravenous or oral omadacycline. For those receiving intravenous omadacycline, a 100 mg IV dose (in 100 mL normal saline solution) infused over 30 minutes at room temperature will be administered. For those receiving oral omadacycline, a single dose of 300 mg oral omadacycline tablet (150 mg tablet x 2) will be administered.

Oral study drug will be administered in the morning in a fasted state with no food or drink except for water at least 6 hours prior to dosing. Fasting is defined as no food, antacids, or multivitamins containing multivalent cations (eg, aluminum, magnesium, calcium, bismuth, iron, or zinc) or drink except water for at least 6 hours before dosing. Subjects will have no food or drink except water for at least 2 hours after dosing and no dairy products, antacids, or other aluminium- or calcium-containing products (eg, vitamins, supplements) for 4 hours after dosing.

A total of 7 blood samples for PK analysis of oral omadacycline and 8 blood samples for iv omadacycline will be collected at specified time points prior to dosing and through 48 hours after dosing. Safety assessments will include monitoring of adverse events (AEs), clinical laboratory test results, vital sign measurements, and physical examination findings.

Subjects will complete a Study Completion visit 4 to 7 days after dose completion. This visit may be performed via phone call to subject's parent/legal authorized representative (LAR) to review ongoing medications and adverse events if the subject has already been discharged from the hospital before Day 4.

Refer to the Schedule of Events ([Appendix 1](#)) for the summary of subject visits and assessments through study completion. The planned length of subject participation in the study is up to 9 days.

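### SAP 8.3 times all IV PK parameters from the end of infusion, in conflict with SAP 8.2; read literally, the infusion-period area is left out of AUC and Tmax is 0.5 h early

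*SAP*

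**What the plan says.** SAP 8.3 sets the clock for parameter estimation: "Actual sampling times (relative to the end of infusion for the IV Treatment) will be used for the estimation of all plasma PK parameters". The same section defines AUC0-48 as "AUC from time 0 to 48 hours postdose, calculated using the linear trapezoidal rule". AUClast and AUC0-inf also start at time 0. CL is the dose divided by AUC0-inf, and Vz is the dose divided by lambda_z times AUC0-inf, both for IV only.

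SAP 8.2 uses the other clock for the individual profiles, which are plotted against "actual time (relative to the start of infusion for the IV Treatment"). The mean profiles use nominal time, also from the start of infusion.

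The IV dose is "infused over 30 minutes at room temperature will be administered" (SAP 3.1). Blood is drawn before the infusion "and at 10 minutes, and 0.5, 1, 2, 8, 24, and 48 hours after the end of the IV infusion" (SAP 8.2). Protocol 7.5.1 secures the data for either clock: "Infusion start and stop times are to be recorded in the source documents and on the eCRF".

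Protocol 12.7.1 and SAP 3.2.1.1 define AUC0-48 as running for 48 hours after dosing. Neither says that dosing time means the end of the infusion. Neither document gives the dose time or infusion length to enter in the software, or says what happens to a pre-dose record that falls at negative time.

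**The concern.** CL as dose over AUC0-inf holds when the AUC covers all the exposure that the dose produced, from the moment drug enters the body. If time 0 is the end of infusion and integration starts there, half an hour of exposure is outside the integral while the whole 100 mg remains in the numerator. The SAP would also disagree with itself: its figures would place a peak half an hour later than its Tmax table.

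AUC0-48, AUClast, AUC0-inf, Tmax, CL and the volume term are listed as primary endpoints (SAP 3.2.1.1). The rule applies to every IV subject, planned as 20 of 40 (Protocol 7.4), so it does not average out with more subjects. As the text stands, two competent analysts could report different IV primary endpoints from the same data.

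**Working it through.** The documents state no figure for this point. Two steps need no PK assumption and one does.

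**Inputs from the documents**
- Infusion length: 0.5 h nominal (SAP 3.1).
- IV samples: 0.167, 0.5, 1, 2, 8, 24 and 48 h after the end of infusion (SAP 8.2), which is 0.667, 1, 1.5, 2.5, 8.5, 24.5 and 48.5 h after its start.
- Pre-dose sample: "At least 15 minutes prior to infusion of IV omadacycline 100 mg", so at or before -0.25 - 0.5 = -0.75 h on the end-of-infusion clock.
- BLQ "values before the first quantifiable concentration will be treated as zero" (SAP 8.1).
- Linear trapezoidal rule (SAP 8.3).

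**Step 1: Tmax and the AUC0-48 window.** For a peak at the 10-minute sample, Tmax is 0.167 h on the end clock and 0.167 + 0.5 = 0.667 h on the start clock. The shift equals the infusion duration. On the end clock, 0 to 48 h corresponds to 0.5 to 48.5 h from the start of dosing.

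**Step 2: the AUC difference.** Let C1 be the 10-minute concentration. After that sample, every trapezoid and the extrapolated tail are the same on both clocks, since intervals and concentrations are the same. So AUClast and AUC0-inf differ only in the initial segment:
- Start clock, zero at time 0: 0.5 × 0.667 × C1 = 0.333 h × C1.
- End clock, zero at time 0: 0.5 × 0.167 × C1 = 0.083 h × C1.
- Difference: 0.333 - 0.083 = 0.25 h × C1, lost on the end clock.

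If a concentration C0 at the end of infusion is back-extrapolated instead, the end-clock segment is 0.083 × (C0 + C1), and the loss is 0.25 × C1 - 0.083 × C0.

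Cmax is a concentration, and lambda_z is a slope that a constant time shift leaves alone. Neither changes, and so T1/2 does not either.

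**Step 3: relative size, under assumed PK.** The assumptions are terminal half-life 10, 16 or 24 h, distribution half-life 0.5 or 1 h, and 5, 15 or 25% of AUC in the fast phase: 3 × 2 × 3 = 18 noise-free profiles, with lambda_z from the last three points.

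For a phase with rate constant k and infusion length T, the share of its AUC accrued during the infusion is 1 - (1 - exp(-kT))/(kT), where k = ln 2 / half-life:
- Low end (24 h, 1 h, 5%): 0.05 × 0.155 + 0.95 × 0.0072 = 0.015, or 1.5% of AUC0-inf.
- High end (10 h, 0.5 h, 25%): 0.25 × 0.279 + 0.75 × 0.0171 = 0.083, or 8.3%.

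Noncompartmental results on the SAP's sampling grid, end clock relative to start clock:

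| Value at time 0 on the end clock | Computed AUC |
|---|---|
| Zero | -1.3% to -5.9% |
| Back-extrapolated | -0.8% to -3.5% |

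CL and Vz move by the inverse ratio. With zero at time 0 that is 1/0.987 = 1.013 to 1/0.941 = 1.063, or about 1-6% higher. A wider set of 32 profiles (terminal half-life 6-24 h, one- and two-compartment) gave CL and Vz 0.7% to 8.4% higher and AUC0-48 0.5% to 7.8% lower.

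**Step 4: the same 18 profiles against true CL**

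| Analysis | CL error against truth | CL overstated |
|---|---|---|
| End clock, zero at time 0 | -5.2% to +4.4% | 6 of 18 |
| End clock, back-extrapolated | -6.6% to +2.0% | 3 of 18 |
| Start clock | -9.1% to -1.2% | 0 of 18 |

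The linear rule over the wide 2-8-24-48 h intervals inflates AUC and so pulls CL down on either clock. The end-clock omission works against that.

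**The case against.** The strongest reply is that SAP 8.3 gives only the reference for sampling times. It does not fix the lower limit of integration or the dose time, and it calls the AUC postdose. An analyst who enters the dose at -0.5 h and integrates from there loses no AUC. This stands in part: the loss follows from the literal text and is not certain to happen. But the SAP does not state that setting, and Tmax would still be on the end-of-infusion clock.

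A reader might also infer that CL and Vz will be biased high and AUC biased low. The check does not support that. Against true CL, the end clock overstates in only 6 of 18 assumed profiles, and the start clock with the linear rule is further from truth in 15 of 18. That is a chance cancellation of two errors and no reason to keep the wrong time origin, but it rules out a claim of net bias.

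A reader might further infer that IV results cannot be compared with oral or adult data. CL and Vz are IV only, parameters are summarized separately by treatment and cohort (SAP 8.3), and the time origin of the adult reference appears in neither document. The one supportable statement is that IV AUC0-48 would cover a different window from dosing than oral AUC0-48.

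Finally, the effect is small, in descriptive summaries of 6 to 10 subjects per cell, with no formal comparisons planned (Protocol 12.10). The Tmax shift is recoverable from the recorded infusion times. Both points stand, and they bear on severity.

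**Conclusion.** The concern holds as a wrong and internally inconsistent time origin for IV primary endpoints. Without any PK assumption, Tmax is early by the infusion duration (0.5 h nominal) and disagrees with the SAP's own figures. On the literal reading, IV AUC0-48 covers about 0.5 to 48.5 h from the start of dosing, and AUC omits the infusion period.

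The size of the AUC effect rests wholly on the assumed half-lives and fast-phase fraction: about 1-6% lower AUC and about 1-6% higher CL and Vz than the same analysis on a start-of-infusion clock. It should not be quoted as bias against the true values, nor the loss as inevitable. Cmax, lambda_z and T1/2 are safe. This should be fixed before the analysis is run, but it does not threaten the study.

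**What to change.** In SAP 8.3, replace the end-of-infusion reference with a rule along these lines: for the IV arm, all PK parameters use actual sampling times relative to the start of infusion; the actual infusion duration from the eCRF is entered; and concentration is set to 0 at time 0 when the pre-dose sample is BLQ. Keep the end of infusion only as the label for nominal sampling times. This brings 8.3 into line with 8.2 and with AUC0-48 counted from dosing.

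One consequence to write down: on the start clock the last nominal IV sample is at 48.5 h, so the 48 h endpoint of AUC0-48 is interpolated between 24.5 and 48.5 h.

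The cost is a sentence or two in the SAP. Infusion start and stop times are already collected, so no new data, subjects or procedures are needed.
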